Develop adapted version of VA BIC for patients discharged from an ER		Ĭ	[
after presenting with a mental health concern																l
Pilot adapted version of VA BIC in 3 veterans discharged from an ER																
after presenting with a mental health concern																
Enroll 25 veterans in an RCT of VA BIC																
Clean and analyze data																
Finalize VA BIC manual for patients discharged from an ER																
after presenting with a mental health concern																1
Integration of Findings from VA BIC Use in 4 High-Ris	k C	are	Tra	nsi	tion	Sc	ena	ario	s							
Integrate VA BIC trial data																
Analyze results																
Develop integrated VA BIC manual																1
Write up Manuscript of Work															-	
Dissemination of VA BIC Findings to R	ural	VA	Fa	cili	ties				-							
Identify 3 rural VA facilities interested in implementing VA BIC																
Work with 3 rural VA facilities to adapt VA BIC material locally																
Assist 3 rural VA facilities with implementation of VA BIC																
Track use, success, and challenges of VA BIC implementation by facilities																
Develop a generalizable manual that is adaptable to any rural VA facility																
Propose additional dissemination work to RHRCER								1	1	1						
Manual Development and Testing Work		-	I	ı	I	I	Dis	ser	mina	tion	Wo	ork				
Note. ER = Emergency Room; RCT = Randomized controlled trial; RHRCER= Rural H	ealth	Re	soui	ce (Cent								eside	entia	1	
Substance Treatment Facility; VA = Veterans Affairs; VA BIC = VA Brief Intervention a						_			5	, -	-		-	-		

Statistical Considerations

Statistical Analyses: To maintain blinding, the statistician who is otherwise not directly involved in the study will conduct the analysis based on the intention-to-treat principle. Below, we have outlined the specific analysis plan for assessing each of the primary and secondary aims of interest of this study. We will assess for statistically significant differences in baseline study characteristics such as age, sex, race, and mental health diagnosis, between study arms using *t*-tests for continuous measures and chi-squared tests for dichotomous variables. We will report these results using 95% confidence intervals (CI) and *P*-values. We will define statistical significance as a *P*-value < 0.05. If we identify any variables for which there are significant differences across study arms, we will control for these confounders in the analysis of the aims.

Specific Aim 1: We will generate descriptive summary statistics (e.g., means and standard errors, medians) and graphical displays for the BSS total scores at baseline and at each of the follow-up assessments. For each of the four acute care settings included in our study, we will perform simple statistical tests. First, we will use a repeated measures analysis of variance (ANOVA) test to assess for changes in continuous variables in the first three months after discharge. Second, if the repeated measures ANOVA suggested a significant difference in means across time, we will perform a post-hoc, pair-wise comparison of means at baseline and one- and three-month follow-up using a two-sample t-test.

We will perform a more complex analysis for the entire study sample at the end of the four years because we will have adequate power to do so. The following outlines are specific approach: Based on available evidence, we hypothesize that the VA BIC program plus standard hospital discharge care will lead to a significant reduction in suicidal ideation after discharge from an acute care setting. We believe that the effect of VA BIC on suicidal ideation will be the greatest at the three-month follow-up because the greatest intensity of follow-up care provided through VA BIC occurs within the first three months after discharge. We will generate descriptive summary statistics (e.g., means and standard errors, medians) and graphical displays for the BSS total scores at baseline and at each of the follow-up assessments. Because BSS scores are typically over dispersed, it is not appropriate to use standard parametric statistics. Therefore, we will treat the BSS scores as count data and use negative binomial regression. Specifically, we will use a generalized linear mixed model. We will consider allocation of study arm (categorical measure) and time (continuous measure) as fixed effects. Random effect will be used to account for correlation that arises from repeated measures of the same individual. We will assume a linear effect and model changes in suicidal ideation over time. We will calculate 95% CI and P-values and will define a *P*-value of < 0.05 to be statistically significant. We will use the maximum likelihood ratio to account for any missing data.

Specific Aim 2: First, we will perform an analysis to demonstrate whether there are greater improvements in patient engagement, hopelessness, and perceived connectedness over time in patients assigned to the VA BIC intervention versus control condition at one, three months after discharge. For continuous variables measuring patient engagement (PIH, Hopelessness, Regularity of Care, Continuity of Care across Organizational Boundaries, and Intensity of Care) and perceived connectedness (INQ-15), we will generate descriptive summary statistics (e.g., means and standard errors, medians) and graphical displays for each measure at baseline and at each of the follow-up assessments. Second, using analysis of covariance (ANCOVA), we will calculate mean differences in scores for each of our continuous measures at the one-and three-month follow-up, as well as the associated 95% confidence intervals and *P*-values. For the categorical measure of disruptions in care, we will use chi-squared tests to compare the proportion of patients experiencing disruptions in care between the two study arms at one- month and three-months after discharge.

Specific Aim 3: While suicide deaths and suicide attempts are important clinical endpoints, this single-site trial will not be powered to detect a statistically significant effect between study arms. Furthermore, because we assume that few events will be observed in either arm, we plan to summarize our findings by providing basic descriptive statistics regarding the number of events in each arm at one-and three-month follow-ups.

Randomization: Prior to the start of study enrollment, the statistician will independently prepare allocation cards using a permutated block schedule. The advantage of this approach is that it ensures that an equal number of participants are assigned to each arm.⁵⁶ The statistician will the put these cards into sealed, opaque, numbered envelopes. The box of envelopes will be stored in a locked cabinet in the study coordinator's locked office.

Sample Size: Because of our promising pilot work,¹ we believe it is appropriate to choose suicidal ideation as our primary outcome. In our pilot study, which included nine Veterans undergoing the VA BIC intervention, we found a greater than five-point improvement in the Beck Scale for Suicidal Ideation (BSS) over the three months following inpatient mental health discharge. Five points is a clinically meaningful improvement on the BSS as it represents the mean difference in suicidal ideation between ambulatory and hospitalized psychiatric patients.² Furthermore, with this sample size and level of improvement, we were able to demonstrate a significant difference in improvement in suicidal ideation compared to a matched group of historical controls participating in a post-mental health discharge qualitative study.^{1,3} Therefore, we will have sufficient power to show a clinically meaningful improvement in suicidal ideation overall and for each of the four high-risk care transition scenarios at one and three months after discharge if we enroll a total of 100 veterans (25 per transition scenario) over 3 years.

Study Population and Recruitment

As described in the Specific Aims section, the proposed study will occur over the course of a total of four years with the funding of the study starting October 1, 2019. In year one of the study, we will first conduct a randomized trial of the intervention on Ground East. We made this decision because we have established experience conducting a small pilot of the intervention on the same unit. The first stage of the study will be conducted at the WRJ VAMC and will recruit patients hospitalized on Ground East (GE), the facility's 10-bed inpatient mental health unit. GE staff includes an inpatient psychiatrist and psychologist, nursing staff, a social worker, and trainees from these disciplines. We aim to recruit a total of 25 patients from Ground East. Study staff will communicate on a daily basis (Monday-Friday) with the inpatient treatment team in order to identify potentially eligible patients who can be approached about study participation. The inpatient team and attending psychiatrist will make the determination as to when and whether it is clinically appropriate for study staff to approach potentially eligible patients. After approaching eligible patients, study staff will make them aware of the study and determine if they are interested in participating in the study. If patients are interested in the study, study staff will obtain informed consent using a written informed consent document prior to enrolling the patient into the study. Study staff involved in the recruitment and consent process will be blinded at the time of study allocation. During the course of the study, it will be impossible to blind the VA BIC intervention staff or patients to treatment allocation; however, the outcome assessor will remain blind to study assignment throughout the trial. Patients will be instructed not to reveal their study assignment to the outcome assessor.

Inclusion Criteria:

- Per the unit psychiatrist, hospitalization was due to concerns about acute risk for self-harm including suicidal ideation, suicide attempt, and/or admitting provider deemed the patient was at imminent risk for self-harm;
- Be a Veteran eligible to receive VA services; be 18 years or older; be able to speak English;

Exclusion Criteria:

- Unable to provide informed consent;
- We do not plan to enroll any potentially vulnerable populations including prisoners, institutionalized patients, or involuntarily committed patients.

Informed Consent

Eligible participants who are interested in participating in this study will complete the informed consent process. Study staff will inform the patient about the study and provide them with the informed consent document. Patients will have the option to review the document with their doctor, family, and/or friends prior to signing if they choose. Upon signing, they will be provided with a photocopy of the document. We do not anticipate a waiting period between informing the patient of the study and obtaining informed consent, but participants may choose to wait. To ensure understanding of the study purpose and procedures, the patient will be encouraged to ask questions if there is anything they do not understand. Additionally, the informed consent document is written in easy-to-understand language to facilitate comprehension.

Risks and Side Effects:

Potential Risks

Since the study population is known to be at high risk for suicide and study endpoints include suicidal ideation, suicide attempts, and suicide, these events would be considered anticipated adverse events during the course of this study. Similarly, we also consider that psychiatric hospitalizations or emergency room for worsening psychiatric symptoms or suicidal behavior are anticipated adverse events.

As described above, it is expected that patients may report worsening suicidal ideation or suicidal behaviors at the study assessments (i.e., baseline, one-month, or three-month follow-up) regardless of whether they are assigned to the intervention or control condition. It is also possible that patients assigned to the intervention arm may report worsening suicidal ideation or suicidal behavior during an intervention visit. It is also possible that patients could be seen in the emergency room or be hospitalized because of any of these events. Thus, it is expected for the patients to continue with the study unless the patient requests to be removed from the study. Furthermore, as outlined in our **safety alert protocol (Appendix 3)**, study personnel will immediately follow the safety alert protocol in response to any reports of worsening suicidal ideation or behaviors. If necessary, patients will be connected immediately with required clinical treatment. All patients will continue to have access to standard-of-care treatment during the course of the trial regardless of study assignment. Furthermore, all patients may continue any treatments that they were receiving as part of their routine care prior to enrolling in the study.

Therapeutic Risks

During the trial, the research staff will ask patients questions about how they are feeling and their interactions with other people. Patients will be exposed to these therapeutic risks during the baseline and follow-up assessments at one- and three-month follow-ups. In addition, patients assigned to the intervention condition will also be exposed to these therapeutic risks at the intervention visits (brief education visit plus six contact visits after discharge). Sometimes, patients can feel embarrassed, nervous, bored, or generally uncomfortable when they are asked to answer these types of questions. However, because there are sufficient safeguards in place to mitigate these potential risks, the overall therapeutic risk from this study to enrolled patients is very low.

Research Risk

During the course of the trial, protected health information including name, social security numbers (in order to process participant payments), phone numbers (for contact purposes), sociodemographic information (e.g. age, race), psychiatric diagnoses (e.g. Alcohol Use Disorder, Substance Use Disorder, Depression), mental health treatments received, and psychiatric symptoms (e.g. responses to standardized questionnaires) will be collected from all enrolled patients. Thus, there is some risk that a patient's confidentiality or protected health information could be compromised due to study participation. As there are sufficient safeguards in place to mitigate this risk (see Protection Against Risk below), the overall research risk in this study is very low.

Protection Against Risk

Study Population Safety Risk

At each study assessment time point (i.e., baseline, one-month, and three-month follow-up), patients will be assessed for symptoms of suicidal ideation and suicidal behavior because these are *a priori* study endpoints. In addition, for patients assigned to the intervention, patients may report worsening suicidal ideation or suicidal behavior in the context of the intervention visits. Regardless of whether the patient is assigned to the intervention, the study staff will be ethically bound to take appropriate action if the patient is at imminent risk for self-harm. The safety alert protocol (**Appendix 3**) outlines the process that study staff members will follow in order to ensure the safety and well-being of all enrolled patients regardless of whether they are assigned to the intervention or control condition. In the event that a safety alert is met, the research

staff member will contact [name] (or the mental health physician covering for her) or, if necessary, the patient's mental health provider. As part of this risk assessment, the assessing clinician will immediately complete a comprehensive risk evaluation and determine the most appropriate next level of care for the patient. The next level of care may include psychiatric admission, emergency room referral, or an urgent outpatient appointment with the patient's healthcare provider. Please see **the safety alert protocol (See Appendix 3)** for a full description of all safety alerts and required actions by study staff members.

Therapeutic Risk

Patients will be given ample time to answer questions and complete visits in order to reduce any discomfort they may experience. Patients will also be made aware that if any of the questions make them feel uncomfortable, they should feel free to mention this to the study staff member and have this concern addressed immediately. At any point during a visit, a patient can take a break or refuse to answer a question.

Research Risk

Every effort will be made to ensure that the privacy and confidentiality of the patient is maintained. All study visits will occur in a private office on the WRJ VAMC campus to ensure privacy. If a visit or assessment is done via a phone call, the research staff will conduct the phone call in a private office. All assessments that can be collected electronically will be stored on a secure, password-protected file on a secure, local researcher server. All staff associated with the study will complete required security training prior to the start of the study in order to be permitted access to this server. Furthermore, all study staff will adhere to the required annual training (by the WRJ VAMC) necessary to maintain their access to the server. All paper copies of study-related data, including consent and HIPAA forms, will be kept in a locked file cabinet, in a locked office, dedicated to this study. Only research staff will have access to this locked cabinet.

Benefits:

All patients participating in this trial will receive standard of care and will be able to continue all treatments and mental health care that they would otherwise have access to outside of the study. In addition, depending on study assignment, some patients may receive the VA BIC intervention. The VA BIC is designed to enhance care that patients receive by helping to connect them with available mental health resources and educating them about suicide prevention after psychiatric hospitalization. Although the VA BIC is adapted from a successful suicide prevention strategy (WHO BIC),^{32,34} it is unknown whether the VA BIC significantly reduces suicide risk after psychiatric hospitalization relative to standard discharge practices. The work from this proposed study will be able to more definitively address whether the VA BIC intervention is an effective suicide-prevention strategy in patients following a psychiatric hospitalization. This is important, given that death by suicide after psychiatric hospitalization remains an important problem in the Veteran population despite the VA's multiple suicide-prevention strategies. Since the overall risks associated with this trial are minimal and the anticipated benefits and knowledge to be gained are clinically important, there is sufficient reason to conduct this study.

Protected Health Information:

We will administer several validated instruments to all enrolled patients at baseline and follow-up (one-and three-month follow-ups). These instruments ask various questions related to self-harming thoughts or behavior and social connectedness. We will also ask patients to report on any non-VA healthcare utilization at one- and three-month follow-ups. Demographic data and other baseline characteristics will be collected from the patient's electronic medical record at baseline. Information on VA healthcare utilization will be collected from the patient's electronic medical record at one- and three-month follow-ups. All data will be collected solely for the purposes of this study. All study data will be collected using an electronic data-capture system. These data are stored on a local, secure research server that only study staff will have access to. All paper copies of study-related data, including consent and HIPAA forms, will be kept in a locked file cabinet, in a locked office, dedicated to this study. Only research staff will have access to this locked cabinet.

Multi-Site Study Concerns

In Year 4 of the study, we will identify three rural sites interested in implementing VA BIC and work with these

sites to implement VA BIC locally. Prior to conducting this work, we will submit a study amendment to VINNE.

Resources Available

This project will be conducted at WRJ VAMC. For the first phase of the study, recruitment of 25 participants will take place on Ground East. Over the next phases of the study, we will be recruiting 25 participants from each of the following locations including inpatient medical/surgical services, residential drug treatment program (RRC) and the emergency room. Drs. [name] and [name] will oversee and lead this project with the help of research staff, which includes:

- A VA BIC interventionist (100% Year 1, 2, 3; 50% Year 4)
- A study coordinator (100% all 4 Years)
- A statistician (10%, Year 1, 2, 3; 20% Year 4)
- An independent assessor blinded to study arm (50% in Years 1-3)
- An implementation scientist to aid Drs. [name] and [name] to work with 3 rural VA facilities and develop generalizable materials to disseminate VA BIC broadly in rural VA facilities through future work.

Subject Compensation:

We will compensate enrolled patients as follows: baseline: \$50; one-month follow-up: \$100; three-month follow-up: \$150. This schedule ensures that patients are sufficiently reimbursed for their time and effort in the study. Furthermore, the staggered schedule of higher payments over time accounts for the additional burden of committing to the study for three months. Finally, higher payments have been shown improve study retention, while not being unreasonably coercive.⁵⁷⁻⁵⁸

Privacy and Confidentiality:

Please see Protection Against Risk above.

Data and Safety Monitoring Plan

Monitoring and Interim Analysis Plan: We have formed an independent Data Safety Monitoring Board (DSMB) comprised of [name] (has expertise in ethics and has previously served on a DSMB), [name] (statistician who has experience serving on the Dartmouth-Hitchcock DSMB), and [name] MPH (who has experience in mental health and suicide prevention). The independent DSMB will provide independent data and safety monitoring for this study. The DSMB will meets annually. The DSMB will focus on ensuring safety and feasibility, including participant accrual and retention, adverse events monitoring, and data analyses. Based on these findings, the DSMB may recommend: (1) continued approval (unconditionally or with conditions to be addressed); (2) probation; or (3) possibly termination, if there are problems with enrollment or safety concerns. We will also ask that the DSMB perform an independent, interim statistical analysis on our data on an annual basis. [name] has experience performing these types of analyses. This will allow us to identify whether the treatment has greater benefits or risks than anticipated and make necessary changes to the trial including changing the trial or terminating the trial.

Study Safety & Monitoring:

Enrolled patients will be monitored for any unanticipated problems or adverse events during the course of the study. Unanticipated death possibly related to research will be orally reported to VINNE immediately with a written report submitted via IRBNet within 5 business days. Possibly study-related unanticipated problems involving risk to subjects or others; serious adverse events; and deviations/non-compliance will be reported within 5 business days to VINNE. Adverse events will be reported with continuing review. Information security or privacy incidents will be reported to the ISO or PO within one hour of discovery. As described above, we consider that the following events are anticipated adverse events: suicidal ideation, suicide attempts, suicide, and psychiatric hospitalizations or emergency room for worsening psychiatric symptoms or suicidal behavior.

Reasons for stopping assigned treatment and follow-up:

The following events will be considered reasons to stop assigned treatment and or follow-up of an enrolled patient: (1) death because the patient would no longer be accessible to study staff; or (2) patient requests to withdraw from the study. In the event that the patient is assigned to the intervention, we will ask the

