In **Year 1**, we plan to confirm our pilot findings suggesting that VA BIC is effective in reducing suicide risk after psychiatric hospitalization by conducting a small, randomized trial of VA BIC plus standard care versus standard care alone on the White River Junction (WRJ) VA Medical Center (VAMC) inpatient mental health unit (see Preliminary Studies section below). In addition, we plan to further adapt VA BIC for veterans experiencing three other high-risk care transition scenarios described above. During **Years 2 and 3**, we will sequentially conduct randomized trials of VA BIC plus standard care versus standard care alone for the other three high-risk care transition scenarios. If our findings indicate that VA BIC is an effective intervention in one or more of these high-risk care transition of VA BIC and assisting them with implementation at their sites. These materials would be used for broad dissemination in future work. Based on both our pilot work with the VA BIC and the results of the original international WHO BIC study, we are highly confident that our intervention will be helpful for rural VA facilities in decreasing suicide risk in at least one of the high-risk care transition scenarios. However, we feel that taking the preliminary steps in Years 1-3 will result in the most practical and effective program for rural VA facilities in Year 4.

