collection form to collect information on non-VA treatment. We have already piloted this data collection form in our current pilot study. We will include three measures of continuity of care including intensity of treatment, regularity of care, and continuity of care across organizational boundaries. These measures of continuity of care have been shown to be associated with improved mental health outcomes.⁸ Because the focus of our project is on generating practical clinical results for rural VA facilities rapidly and cost-effectively, we will limit our longitudinal assessment to these outcomes. Finally, travel to appointments is a notable concern for veterans living in rural areas. We will give patients the choice to participate in VA BIC contact visits in-person, by telephone or via VA Video Connect. This approach aligns with the VA's goal to expand the use of telehealth services.

Study Objectives

- 1) To adapt the VA BIC for use during high-risk care transition scenarios including emergency room care, medical hospitalization and acute treatment in a drug dependence rehabilitation program.
- 2) To confirm that the VA BIC is effective at reducing suicidal ideation and other related measures of suicide risk during high-risk care transition scenarios including psychiatric hospitalization, emergency room care, medical hospitalization and residential substance treatment facility.
- 3) To disseminate the VA BIC to other rural VA facilities and assist these facilities with implementing VA BIC at their local sites in order to reduce the burden of suicide in rural veterans during high-risk transition care scenarios.

Our specific aims and hypotheses are as follows.

Specific Aim 1: The primary aim of the study is to determine whether the VA BIC program plus standard discharge care reduces suicidal ideation after discharge from an acute care setting compared to standard discharge care, alone.

Hypothesis: Based on available evidence, we hypothesize that the VA BIC program plus standard discharge care will lead to a significant reduction in suicidal ideation after discharge from an acute care setting. We believe that the effect of VA BIC on suicidal ideation will be the greatest at the three-month follow-up because the greatest intensity of follow-up care provided through VA BIC occurs within the first three months after discharge.

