Overview of the VA BIC Intervention and RCT Design

As shown in **Figure 1 (see previous page)**, to test the aforementioned hypotheses, we propose to conduct a single-site, assessor-blinded RCT at the WRJ VAMC comparing the VA BIC plus standard psychiatric hospital discharge care to standard psychiatric hospital discharge care alone. The trial will enroll patients 18 years and older who are being discharged from the WRJ VAMC inpatient mental health unit. The primary aim is to determine whether the VA BIC reduces suicidal ideation at one and three months after psychiatric hospitalization. The secondary aim is to evaluate the impact of VA BIC on other important measures of suicide risk including hopelessness, connectedness, fatal/non-fatal suicide attempts and treatment engagement.

Baseline Assessment and Randomization: Prior to the start of study enrollment, the statistician will independently prepare allocation cards using a permutated block schedule. The statistician will the put these cards into sealed, opaque, numbered envelopes. The box of envelopes will be stored in a locked cabinet in the study coordinator's locked office.

The study coordinator will meet with each eligible patient in a private room on GE around the time of discharge. The study coordinator will obtain informed consent from the patient and then administer the baseline assessments, which are described under the outcome measures (see below). The baseline visit will take approximately 90 minutes to complete. After obtaining consent and completing the baseline assessment, the study coordinator will take the next numbered envelope from the box (described above) and open the envelope to determine the patient's assignment. In the event that the patient has been assigned to the intervention, the study coordinator will notify the VA BIC intervention staff in order that the intervention staff can initiate the intervention. Otherwise, the patient will be informed that they have been assigned to usual care.

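### The primary aim spans two time points, four settings and a pooled model, all at P < 0.05 with no single primary test; if the setting t-tests compare arms and the ANOVA gate is ignored, the chance of at least one false finding of benefit is about 10% to 17%

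*Combined protocol and SAP*

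**What the plan says.** In Overview of the VA BIC Intervention and RCT Design, the primary aim for the Ground East trial is to determine whether VA BIC "reduces suicidal ideation at one and three months after psychiatric hospitalization". The two time points stand on an equal footing. The hypothesis under Specific Aim 1, repeated in Statistical Considerations, adds "We believe that the effect of VA BIC on suicidal ideation will be the greatest at the three-month follow-up". That is an expectation about where the effect will lie. It does not designate a primary time point.

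Statistical Analyses sets one general threshold: "We will define statistical significance as a *P*-value < 0.05". Under Specific Aim 1, "For each of the four acute care settings included in our study, we will perform simple statistical tests". The first of these is a repeated measures ANOVA. Then, "if the repeated measures ANOVA suggested a significant difference in means across time, we will perform a post-hoc, pair-wise comparison of means", covering baseline, one month and three months and using a two-sample t-test. After four years the whole sample is analysed with a negative binomial mixed model that has arm and linear time as fixed effects. For this model, too, the plan "will define a *P*-value of < 0.05 to be statistically significant".

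Specific Aims/Purpose ties the settings together: "If our findings indicate that VA BIC is an effective intervention in one or more of these high-risk care transition". The rest of that sentence is incomplete in the available text. The Sample Size section claims sufficient power overall and in every setting at both time points, with 100 veterans (25 per setting). The plan contains no multiplicity adjustment, testing hierarchy or named primary analysis.

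**The concern.** A reader cannot tell which P-value answers the primary aim. It could be the one-month or the three-month comparison, in any of four settings or in the pooled sample. When several results can each be read as the answer and each is judged at 0.05, an ineffective intervention has more than the nominal chance of producing one that looks favourable. The plan intends to guide rural facilities towards the populations most likely to benefit, and Year 4 includes spreading VA BIC to three facilities. An isolated chance result could therefore be cited as evidence that VA BIC works in a given setting.

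The problem is present even in the one trial that this version opens: Ground East alone has two equal time points.

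**Working it through.** **The plan's own figure.** The plan states no overall error rate, so there is none to reproduce. Its sample size cannot be re-derived either, because no standard deviation, target power or dropout rate is given.

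**Inputs from the plan.** Threshold 0.05 (Statistical Analyses); four settings and a two-sample t-test (Specific Aim 1); two follow-up times (primary aim); 25 per setting with equal allocation (Sample Size; Randomization), so about 13 versus 12.

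**Assumptions.** Tests are two-sided (the plan does not say), so the chance of a false result in favour of VA BIC is 0.025 per test. The t-tests compare arms. Settings are independent. The correlation r between the one-month and three-month test statistics is 0.5 to 0.7.

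**Step 1: one time point, four settings, no gate.**
- False benefit: 1 − 0.975^4 = 0.096.
- Either direction: 1 − 0.95^4 = 0.185.

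**Step 2: two time points within one setting (Ground East alone), no gate.** The chance of at least one false benefit is 1 − Φ₂(1.96, 1.96; r), where Φ₂ is the bivariate normal distribution function.
- r = 0.5: 0.0454.
- r = 0.7: 0.0417.

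Counting either direction, these become 0.0907 and 0.0835.

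**Step 3: two time points, four settings, no gate.**
- False benefit: 1 − (1 − 0.0454)^4 = 0.170 and 1 − (1 − 0.0417)^4 = 0.157.
- Either direction: 1 − (1 − 0.0907)^4 = 0.316 and 1 − (1 − 0.0835)^4 = 0.294.
- Limit for eight independent tests: 1 − 0.975^8 = 0.183 for benefit and 1 − 0.95^8 = 0.337 in either direction.

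**Step 4: the ANOVA gate.** This was simulated with 13 versus 12 patients, normal data, equal correlation of 0.3 to 0.7 between assessments, an assumed SD of 7 and 4,000 trials per case. VA BIC had no effect. Rates over four settings were:

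| What the gate tests | Course in both arms | False benefit | Either direction |
|---|---|---|---|
| Means across time | 5-point improvement | 15–17% | 28–30% |
| Means across time | No change | about 1% | 1–2% |
| Arm by time | Either of the above | 2–5% | 4–9% |

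The wording describes the first column's first entry, a test across time. Patients enter during a hospitalization for acute self-harm risk, so improvement in both arms is plausible. In that case the gate opens almost regardless of treatment.

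**Outside these figures.** The pooled model and the annual interim analyses, for which no error-spending rule is stated, are not counted.

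**The case against.** Several objections carry weight.

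- **The tests are gated.** It would be wrong to say that each setting and time point is simply tested at 0.05. The t-tests follow only a significant ANOVA, and gated rates run from about 1% to 30% in either direction, depending on what the gate tests and how patients fare. The documents do not fix one figure.
- **The grid of eight between-arm tests is inferred.** The post-hoc step follows a test across time and does not mention arms. The two-sample test suggests arms, but the text could mean comparisons between time points.
- **A 19% to 32% chance of falsely calling VA BIC effective.** A reader might infer this from the four-by-two layout. The documents do not support it: that range counts results in either direction, including those showing VA BIC to be worse, and it ignores the gate.
- **One significant setting triggers dissemination.** A reader might infer this too. The sentence about one or more scenarios is incomplete as available and gives no P-value criterion. Study Objectives and the Year 4 deliverables list dissemination without that condition, after an integrated analysis.
- **The settings are sequential trials with separately adapted interventions**, and only Ground East is open now. Whether such trials need joint error control is disputed.

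The last objection is a good reason not to require a formal correction across settings. It does not remove the need for one primary time point in each trial and one primary contrast overall. The expectation of a greatest effect at three months does not fill the gap, because the primary aim still names both times.

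**Conclusion.** The concern holds in a limited form. The plan names no primary time point, primary analysis or testing order for its primary aim. With two-sided tests that compare arms and no gate, the chance of at least one false finding of benefit across four settings is about 10% with one time point and 16% to 17% with two. Counting either direction, the span is 19% to 32%. For Ground East alone it is about 4% to 5%, against a nominal 2.5%.

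These figures rest on the assumed correlation of 0.5 to 0.7, on independent settings and on an inferred reading of the t-tests. The ANOVA gate lowers them little if both arms improve after discharge. It lowers them substantially if neither arm changes or if it is in fact an arm-by-time test. That uncertainty is itself a reason to say which test decides the aim.

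**What to change.** Name the between-arm difference in BSS at three months as the single primary contrast, estimated in the pooled model. The plan's own hypothesis supports that choice. The model as described lists arm and continuous time but no arm-by-time term, so it would not yield this contrast directly. Add the interaction, or treat time as categorical with an arm-by-time term, and state how the contrast will be expressed.

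In each setting's own analysis, also make three months the primary time point, and say that the comparison is between arms. Report one-month and setting-specific results as secondary estimates with 95% confidence intervals, and state that no setting will be declared effective on an isolated P < 0.05.

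With one pre-specified contrast at two-sided 0.05, the false-benefit rate for the primary aim is the nominal 2.5%, before any allowance for interim looks.

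The cost is revised wording in the primary aim and Specific Aim 1, plus one change to the model specification. No patients or visits are added. The downside is that one-month and single-setting results no longer count as primary evidence. The change is easiest now, while the other three settings still await amendments.
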